## 1.0 Objectives / Specific Aims

Aim 1. Conduct feasibility testing of a mobile health (mHealth) app intervention (MATADORS) among a population of youth with asthma and obesity randomized to the intervention (n = 15) or control (n = 15) group.

Aim 2. Obtain estimates of variability and describe preliminary outcomes of MATADORS on fatigue, pain, self-efficacy, anxiety, sleep, depression, and quality of life measured at baseline, week 4, and an 8-week follow-up period.

## 2.0 Background

Youth with one or more chronic diseases (i.e., multimorbidity) are at increased risk of morbidity and mortality as they enter their adult years . Recent increases in incidence of both asthma and obesity in youth correspond to increased health care use and subsequent health complications , as well as potentially iatrogenic parental and self-imposed limitations on activities due to respiratory symptom exacerbation and fatigue. Physical inactivity and increased steroid-based treatment of asthma symptoms contribute to increased weight gain, creating a problematic cycle that underscores the need to consider these two increasingly prevalent conditions together, as provider and caregiver efforts to address asthma (e.g., steroid treatment, restricted activity, respectively) may exacerbate weight gain and symptoms of obesity.

Research and clinical care for non-communicable diseases (NCDs), which contribute to 71% of deaths globally , are often focused on a single disease approach . Failure to address the complexities and compounded influence of multimorbidity affects quality of life, healthcare utilization, increases disease burden, and contributes to premature death . As asthma and obesity are among the most common chronic diseases, it is important for scientists to develop interventions that reduce the overall burden of each disease and the confluence of the two together .

Current pharmacological and behavioral treatment approaches for asthma and obesity are complex, multi-faceted, demanding, and often result in high rates of non-adherence and non-adoption . Building on our team's prior work to enhance medication adherence via mobile health with children and youth and building on our expertise in weight management of children and youth through community-engaged research, we intend to develop a low-cost, easy to use and readily available MATADORS mHealth intervention that leverages key motivational enhancement (ME) principles using a behavioral activation (BA) framework to guide this intervention.

## 3.0 Intervention to be studied

MATADORS is a multi-component self-management intervention for youth with asthma and obesity that will be delivered via mobile device over a 4-week period and will include tailored content based on the existing SAMS (medication inhaler adherence for children with high-risk asthma) and SELFY (family-centered symptom self-management for children with sickle cell disease) mobile health applications and participation input from Phase I of this study. Participants randomized to the control arm (n = 15) will be enrolled in the existing SAMS symptom tracking and EMA assessment program to include baseline assessment, EMA symptom reporting, and repeated measures at 4 & 8 weeks. Participants randomized to the intervention arm (n = 15) will have continuous access to educational content within the app and weekly nurse-guided support available through videoconferencing support and text messaging to promote engagement. Intervention procedures will include symptom monitoring through self-report and completion of measures (Table 1), accessing of educational content, engagement with study team to increase engagement, use of activity trackers, and photo/voice/video diary entries completed through the app. At study completion, youth and their primary caregivers from both the intervention and control groups will complete an end of study interview.

## 4.0 Study Endpoints

Study endpoints include:

- Successful completed of the 8-week study
- Participant consent withdrawal

- PI termination due to lack of adherence to the protocol
- Withdrawal due to adverse event
- Lost to follow-up

## 5.0 Inclusion and Exclusion Criteria/ Study Population

### *Youth-Caregiver Dyad Inclusion Criteria:*

- Male and female youth aged 10 – 17 years
- Adult primary caregiver
- English speaking
- Youth diagnosis of asthma
- Youth Body Mass Index at or above the 85th percentile for age and sex based on the Centers for Disease Control (CDC) growth charts
- Must own a smartphone (iOS) with working Wi-Fi access and/or cellular data plan

### *Youth-Caregiver Dyad Exclusion Criteria:*

- Diagnosis of cognitive impairment
- Inability or unwillingness of youth participant to assent and/or primary caregiver/legal guardian/representative to give informed consent.
- Inability or unwillingness to participate in the end-of-study interview session.

### Inclusion of a diverse population

Participants from all racial and ethnic backgrounds will be approached and invited to participate as research participants.

## 6.0 Number of Subjects

The target enrollment for this study is N=60. This includes 30 youth (10-17 years old) and their primary adult caregivers.

## 7.0 Setting

Study procedures will take place using virtually using communication means such as telephone, email or meeting platforms, such as Microsoft Teams or DoxyMe. In-person informed consent may be collected in a private MUSC clinic or office space, pending participant preference and current social distancing requirements. As an alternative to in-person consent, participants will be offered the option to provide e-consent via the MUSC e-consent REDCap template or DoxyMe. Initial study procedures (consent, basic demographic and baseline measures, and study instructions) and measure completion at 4-week intervention and 8-week follow-up will be completed remotely using REDCap. Post-exit interviews will be conducted via Microsoft Teams or DoxyMe.

## 8.0 Recruitment Methods

This study will use the following recruitment strategies:

- Youth and caregivers that participated in Phase I of the study and agreed to be re-contacted by the researchers regarding volunteering in Phase II will be approached about this part of the study.
- Youth and their caregivers that are seen in the clinics of research team members that are MUSC clinicians will be approached and given a study flyer.
- A BMIC query through honest broker services will be conducted and used to identify and contact families of youth that meet the study inclusion criteria and that have not opted-out of being contacted. Researchers will use a telephone script and contact with these individuals will follow MUSC policies and procedures for contacting patients for research purposes.

- Study flyers will also be placed in clinic and public areas throughout the Medical University of South Carolina Enterprise.
- Flyers, advertisements, and study information will be posted on social media channels, on Research Match, and will be sent to professional and community-based organizations focused on care of youth with asthma or obesity.

## 9.0 Consent Process

Research activities will not be conducted without the caregiver's written informed consent and youth's written assent. One caregiver per youth will be consented to participate in the study. The caregiver consenting and participating in this study will be the child's self-identified primary caregiver. Informed consent will be conducted by an approved member of the study team. As an alternative to in-person consent, participants will be offered the option to provide e-consent via the MUSC e-consent REDCap template or DoxyMe.

Prior to the consent meeting, potential participants will have already spoken with study personnel by phone or in person at a clinic visit, will have been introduced to the study and its demands, had initial questions answered, and will have received a copy of the informed consent for their review. Participants who are further interested will be allowed as much time as needed to read and review the consent document in the privacy of their own home or at a place of their choosing. They will be provided with the telephone and email contact details for study personnel, should they have any questions before to the consent meeting. Prior to providing their physical e-consent, IRB-approved study personnel will coordinate with participant so as to be on the telephone, online, or in-person (when appropriate given social distancing and current COVID-19 requirements/guidance) and be available to further answer any questions that they may have during the e-consent process.

After reviewing the consent document, the patient will be given the opportunity to ask any questions about the study that they may have. Participants will be requested to demonstrate what is expected from them should they agree to enroll in the study through verbal questioning of their understanding of study procedures and risks. Prior to consenting, all questions will be resolved to the patient's satisfaction. If a participant does not appear to understand the information contained within the Consent document or of what is expected of them as a study subject, then the study coordinator will review the consent document again with the participant. If after this second review, the subject does not demonstrate an understanding, they will not be enrolled in the study. Only participants, with no observed cognitive impairment, will be consented and enrolled into the study.

The consent form will meet the requirements of the Code of Federal Regulations and the MUSC Institutional Review Board; and, include the following elements:

- The purpose, nature, and objectives, potential risks and benefits of the intended study.
- The length of study and the likely follow-up required.
- The name and a contact of the investigator(s) responsible for the protocol.
- The right of the participant to accept or refuse study interactions and to withdraw from participation at any time.

All consented subjects will be given a copy of their executed and countersigned Consent form. The researchers will maintain a means of contact with all enrolled study participants in the eventuality that reconsenting of currently enrolled participants is needed and/or the disclosure of new study information is warranted to previously enrolled participants.

## 10.0 Study Design / Methods

This feasibility study is an 8-week, longitudinal randomized controlled trial (RCT) with 3 study visits (baseline, week-4, and week-8) among youth 10-17 years old (n=30) with asthma and >85% BMI and their primary caregivers (n=30). Eligible participants that agree to consent, will be randomized 1:1 into the MATADORS intervention or control group. Randomization will be performed by the study coordinator in REDCap utilizing a

scheme generated by the study biostatistician. The PI will be blinded to study allocation until the end of study follow-up interview. Participants randomized to the control arm (n = 15) will be enrolled in the existing SAMS symptom tracking and EMA assessment program to include baseline assessment, EMA symptom reporting, and repeated measures at 4 & 8 weeks. Intervention participants (n = 15) will have continuous access to educational content within the app and weekly nurse-guided support available through videoconferencing support and text messaging to promote engagement. Intervention procedures will include symptom monitoring through self-report and completion of measures (Table 1), accessing of educational content, engagement with study team to increase intervention engagement, use of activity trackers, and photo/voice/video diary entries completed through the app. During engagement with study team, participants will receive feedback on the one-time video inhaler technique submitted via the MATADORS app. At study completion, youth and primary caregivers will complete an end of study interview. Interviews will be audio-recorded and professionally transcribed.

## Data Collection/Measures

Data collection approaches, instruments, and interventions are outlined in Table 1. Primary intervention measures will be collected at baseline, end of study (week 4), and the week 8 follow-up.

Table 1. Data Collection/Measurement/Instruments/Interventions/Time Points

| Data Collection                 | Measures   | Data Sources  | Time Point   |
|---------------------------------|--|---|--|
| Demographics/Clinical           | Age, date of birth, gender, race, ethnicity, education, insurance, urban/rural residence, caregiver demographics, family characteristics, diagnoses, medications, Short Assessment of Health Literacy-English   | Medical record review, participant interview  | Baseline   |
| Exit Interview                  | Semi-structured interviews   | Dyadic and 1:1 participant interviews   | Post intervention follow-up (week 8 +/- 7 days)                |
| Reach:
Sample
Recruitment | Monitoring of sample representativeness, types of recruitment activities, rate of recruitment, % eligible, and consented   | Recruitment tracking form   | Study initiation, daily, and study end                         |
| Efficacy:                       | PROMIS Pediatric Fatigue 10a 
Self-Efficacy for Managing Chronic Disease-6 item
Neuro-QOL Item Bank v2.1-Pediatric Fatigue
PROMIS Pediatric Item Bank v2.0-Pain Interference
Neuro-QOL Item Bank v.1.0-Pediatric Pain-Short Form
PROMIS Pediatric Emotional Distress: Anxiety 
PROMIS Pediatric Emotional Distress: Depression 
# days reporting symptoms (fatigue, pain, anxiety, depression)
Self-report medication adherence (rescue/controller) from SAMs study
Self-report missed school/work/activity
Activity tracker-step count & sleep patterns (hours per day)
Physical activity patterns (# of minutes active/day per Fitbit)
Inability to concentrate/sleepiness during the day
Pediatric Quality of Life Inventory 3.0 Asthma Module 
Asthma Belief Survey 
Asthma Control Test
Inhaler technique video (one time video during 4 week study period) | Participant interviews, self-report, diary entries (video/voice/photo entries), and activity tracker data | Baseline, daily, end of study, and post-intervention follow-up |

|                        |   |   |   |
|------------------------|---|---|---|
| Adoption:       | # days reporting symptoms (fatigue, pain, anxiety, depression)
# times educational modules accessed (time in minutes)
# diary entries
Activity tracker-step count
Activity-self report (PA)           | Tracking forms, activity tracker reports, diaries, app access counts, symptom reporting | Daily   |
| Implementation: | # problems with mobile device/app/fitness tracker; fidelity to intervention; participant/caregiver recommendations; acceptability of intervention; participant burden (time) spent completing dependent measures. | Tracking forms and study team meetings  | End of study interviews and satisfaction questionnaires |
| Maintenance:    | # youth who would continue post intervention; youth & caregiver perception of intervention; recommendations for revision  | Youth-caregiver end of study interview  | End of study interviews and satisfaction questionnaires |

Measures of feasibility, including recruitment, reach, adherence, satisfaction, participant burden of data collection procedures, and fidelity to interventions will be evaluated. Quantitative measures will be entered into REDCap and analyzed using SPSS. Univariate descriptive statistics and frequency distributions will be calculated, as appropriate, for all variables. Demographic variables will be described via measures of central tendency (mean, median), variability, and frequency distributions, as appropriate. Demographic and clinical characteristics from completers/non-adherent/non-completers will be compared to better understand and describe the population. Confidence intervals (95%) will be used to estimate dichotomous outcomes (e.g., proportion completing intervention, proportion adherent to the intervention, proportion providing daily symptom reporting and diary entries) and continuous feasibility measures (e.g., satisfaction scores and end of study interview). Qualitative data from end of study interviews and video/voice diaries will be analyzed using directed content analysis and transcripts will be entered into MAXQDA Analytics Pro software. A priori and emergent codes will be analyzed using the RE-AIM theoretical framework.

**Participant Compensation:** Aim 2 Control participant dyads (n =15) will receive checks for completion of study activities (\$30 each for baseline data collection and training for both youth and caregiver participants; \$25 for each participant for weeks 4 & 8 measures; \$25 for each member of the dyad for post-study key informant interviews; \$10 for a one-time video upload of inhaler technique; and up to \$1/day for symptom reporting/EMA entries and Fitbit usage x 30 days maximum) (control group youth maximum remuneration = \$175/participant; control parent maximum remuneration = \$105). Intervention participant dyads (n=15) will receive (\$30 each for baseline data collection and training for both youth and parent participants; \$25 each for weeks 4 & 8 measures; \$25 for each member of the dyad for post-study key informant interviews; \$10 for a one-time video upload of inhaler technique; and up to \$4/day for symptom reporting/EMA entries, medication reporting, Fitbit usage, and video/voice/photo diary entries x 30 days maximum) (intervention group youth maximum remuneration = \$235/participant; intervention group caregiver maximum remuneration = \$105).

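### Aim 2 scores get univariate descriptives only: no baseline-adjusted arm difference, adjusted SD or between-visit correlation is planned, and no confidence interval for any of these scores

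*Combined protocol and SAP*

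**What the plan says.** Section 1.0 sets Aim 2: "Obtain estimates of variability and describe preliminary outcomes of MATADORS on fatigue, pain, self-efficacy, anxiety, sleep, depression, and quality of life", at baseline, week 4 and week 8. Section 10.0 makes the study a randomised comparison: "Eligible participants that agree to consent, will be randomized 1:1 into the MATADORS intervention or control group", with 15 youth per arm. On timing, Data Collection/Measures says "Primary intervention measures will be collected at baseline, end of study (week 4), and the week 8 follow-up", and Table 1 files the Aim 2 instruments under its efficacy row.

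The analysis paragraph after Table 1 makes three provisions for quantitative data:

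- For everything: "Univariate descriptive statistics and frequency distributions will be calculated, as appropriate, for all variables".
- For groups: "Demographic and clinical characteristics from completers/non-adherent/non-completers will be compared to better understand and describe the population". This comparison is by completion and adherence status, not by randomised arm.
- For intervals: 95% CIs for dichotomous outcomes, such as the proportion completing, and for continuous measures of feasibility, such as satisfaction.

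Section 14.0 keeps the data already collected from youth who withdraw, under intention to treat. Section 4.0 lists "Lost to follow-up" among the ways participation can end.

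**The concern.** A randomised control arm is there so that MATADORS can be set against it. The plan names no summary of the Aim 2 scores by arm, no difference between arms and no interval. At 15 per arm, a chance gap between two means can look like an effect unless its uncertainty is shown beside it.

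The promise to estimate variability is only partly met. The SD at one visit is neither the SD of change nor the SD left after baseline adjustment. Moving from one to the others needs the correlation between baseline and follow-up, which univariate summaries do not give.

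All three visits are stored, so nothing is lost for good. But if these quantities are worked out later, the choice between unadjusted, change-score and baseline-adjusted results is made with the data in view, for eight questionnaires at two follow-up visits.

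**Working it through.** The plan gives no SD, correlation, effect size, power or dropout figure, so there is no stated result to reproduce beyond the counts: 15 + 15 = 30 youth, and 30 youth + 30 caregivers = 60, which agree.

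**Inputs.** From the documents: n = 15 per arm, 1:1 allocation, two follow-up visits. Assumed: baseline-to-follow-up correlation r = 0.3, 0.5 or 0.7; equal SDs across visits; and 12 per arm observed as an example of loss. Results are in units of the single-visit SD.

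**1. One SD does not give the others.**

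| r | Change SD, √(2(1 − r)) | Baseline-adjusted SD, √(1 − r²) |
|---|---|---|
| 0.3 | √1.40 = 1.18 | √0.91 = 0.95 |
| 0.5 | √1.00 = 1.00 | √0.75 = 0.87 |
| 0.7 | √0.60 = 0.77 | √0.51 = 0.71 |

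**2. 95% CI half-width for an arm difference.** Unadjusted: t(2n − 2) × √(2/n). Baseline-adjusted: t(2n − 3) × √(2/n) × √(1 − r²), leaving out the small extra term for chance baseline imbalance.

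| Observed per arm | Unadjusted | Adjusted, r = 0.3 | r = 0.5 | r = 0.7 |
|---|---|---|---|---|
| 15 | 2.048 × 0.365 = 0.75 | 0.71 | 0.65 | 0.54 |
| 12 | 2.074 × 0.408 = 0.85 | 0.81 | 0.74 | 0.61 |

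**3. Chance gaps.** With 15 per arm the standard error of an unadjusted difference is √(2/15) = 0.365 SD. With no true effect, the chance of a gap of at least 0.5 SD either way is 2 × (1 − Φ(0.5/0.365)), or about 17% per comparison (normal approximation).

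**4. Precision of the variability estimates.** For the residual SD the 95% limits are the estimate times √(df/χ²): 0.79 to 1.36 times with 27 df (15 per arm), and 0.77 to 1.43 times with 21 df (12 per arm). For an observed pooled within-arm r of 0.5, the limits are tanh(0.549 ± 1.96/√(N − 4)): 0.16 to 0.73 at N = 30, and 0.11 to 0.76 at N = 24. Both need intervals to be usable.

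**5. Number of estimates.** Table 1 has two fatigue and two pain questionnaires, and one each for self-efficacy, anxiety, depression and quality of life: 8 × 2 follow-ups = 16 arm differences. With one instrument per domain it is 6 × 2 = 12. With no true effect, 16 × 0.05 = 0.8 (or 12 × 0.05 = 0.6) of the intervals are expected to exclude zero, whatever the correlation between them.

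**The case against.** The strongest reply is that this is a feasibility study with a descriptive aim. The documents state no hypothesis, no power and no plan to size a later trial, and descriptive statistics for all variables would ordinarily include an SD. Much of this stands, and it limits the point in four ways.

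- A reader might infer that the plan delivers no variability at all, or that descriptives cannot yield a change SD or an arm difference. Neither follows. A change score is a derived variable that can be summarised like any other, and arm means, SDs and counts are enough for an unadjusted difference and its interval. The plan simply does not say that it will tabulate by arm or use change scores. What it cannot supply is the baseline-adjusted difference, the adjusted SD and the correlation.
- A reader might infer that leaving out a hypothesis test is a fault. In a feasibility study it is not.
- A reader might infer a serious gap over missing scores. Descriptive summaries use the observed scores and need no imputation model, Section 14.0 keeps what was collected, and the proportion completing has a planned CI. It remains only to show the numbers observed and to state a rule for any added model.
- A reader might infer from Section 10.0, where controls "will be enrolled in the existing SAMS symptom tracking and EMA assessment program to include baseline assessment", that baseline follows allocation. That phrase lists what the programme contains, not the order of events, and Section 7.0 groups baseline measures with consent among the first procedures. The order merits a clear statement, but the text does not show an error.

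It is also fair that adding 16 intervals creates its own risk of over-reading. That is a reason to label them plainly. Bare arm means carry the same uncertainty without showing it.

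**Conclusion.** The point holds as a gap between Aim 2 and its analysis that is cheap to close. As written, the randomised three-visit design yields no planned baseline-adjusted arm difference, adjusted SD or between-visit correlation for the Aim 2 scores, and no interval for any of them. Aim 1 is unaffected, and the data needed are already to be collected.

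An interval reaching roughly half to three-quarters of an SD either side of an arm difference, in the best case of no missing scores, is wide enough that means alone could mislead. The adjusted figures rest on the assumed correlations and equal SDs. At r = 0.3 adjustment gains little (0.71 against 0.75 SD); at r = 0.7 it gains a good deal (0.54 SD). The documents do not support any stronger conclusion, such as that Aim 2 cannot be met or that an efficacy test is required.

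**What to change.** Add to the analysis paragraph in Section 10.0, for each Aim 2 questionnaire:

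- (a) The number observed, mean and SD by randomised arm and visit, and the mean and SD of change from baseline.
- (b) The baseline-adjusted arm difference at week 4 and at week 8 with a 95% CI, by one fixed method: ANCOVA at each visit on the baseline score, with all youth who have an observed score analysed in their assigned arm and no imputation.
- (c) The pooled within-arm residual SD and the baseline-to-follow-up correlation, each with a 95% CI.

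Label all of this as estimation, with no tests and no efficacy conclusion. Adjust for baseline only where the measure was completed before allocation, and state that order in Section 10.0. Summarise tracker outcomes, including sleep hours, by arm without baseline adjustment, because Section 18.0 has trackers handed out once the group is assigned.

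The cost is a paragraph of text and modest SPSS work, with no new participants, visits or questionnaires. The downside is 16 wide exploratory intervals, or 12 if one instrument each is named for fatigue and pain. The report should say that about 0.8 (or 0.6) of them would be expected to exclude zero by chance if there were no true effect.
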